	9.1 Informed Consent/Assent Process (in Case of a Minor or Others Unable to Consent for Themselves).....	18
10	Literature References.....	19

SUPPLEMENTS/APPENDICES

A.1 Informed consent for participation in TESTsmART Aim 1 (English and Kiswahili)

A.2 Questionnaire for participants

List of Abbreviations

ACT	Artemisinin Combination Therapy
AE	Adverse Event
CFR	Code of Federal Regulations
CIOMS	Council for International Organizations of Medical Sciences
CRF	Case Report Form
CHW	Community Health Worker
DFID	Department for International Development, UK
DMID	Division of Microbiology and Infectious Diseases, NIAID, NIH, DHHS
DSMB	Data and Safety Monitoring Board
FWA	Federal-Wide Assurance
GCP	Good Clinical Practice
GEE	Generalized Estimating Equation
ICF	Informed Consent Form
ICH	International Conference on Harmonisation
ID	Identification
IEC	Independent or Institutional Ethics Committee
IRB	Institutional Review Board
ISM	Independent Safety Monitor
JAMA	Journal of the American Medical Association
MOP	Manual of Procedures
N	Number (typically refers to subjects)
NEJM	New England Journal of Medicine
NIAID	National Institute of Allergy and Infectious Diseases, NIH, DHHS
NIH	National Institutes of Health
OCRA	Office of Clinical Research Affairs, DMID, NIAID, NIH, DHHS
OHRP	Office for Human Research Protections
ORA	Office of Regulatory Affairs, DMID, NIAID, NIH, DHHS
PI	Principal Investigator
RA	Research Assistant
RD	Risk Difference
RDT	Rapid Diagnostic Test
RR	Risk Ratio
SAE	Serious Adverse Event
SMC	Safety Monitoring Committee
SOP	Standard Operating Procedure
USAID	United States Agency for International Development
WHO	World Health Organization

- Title:** A randomized experiment of malaria diagnostic testing and conditional subsidies to target ACTs in the retail sector: the TESTsmART trial AIM 1
- Population:** We will enroll 840 participants and allocate them to four arms in equal proportions. Participants who are seeking treatment for acute, malaria-like illness will be recruited at medicine retail outlets in western Kenya. Eligible participants are >1 year of age seeking treatment for themselves or present with their parent/guardian at the time of recruitment. Individuals with signs of severe disease will not be eligible
- Number of Sites:** Webuye West, Webuye East and Kiminini in western Kenya.
- Study Duration:** 12 months
- Subject Duration:** 30-45 minutes. Cross-sectional study with no follow-up
- Objectives:** This objective of this experiment is to identify the combination of RDT and conditional (diagnosis-dependent) ACT subsidies that maximize the percent of clients receiving an RDT. We will test two different RDT price levels and two discounted ACT price levels in a factorial design. ACT discounts are conditional on a positive RDT result.
- The primary outcome measure is the decision to purchase an RDT before purchasing a drug.
- Secondary outcome measures are:
1. Decision to purchase an ACT stratified by testing status
 - a. Positive mRDT
 - b. Negative mRDT
 - c. No malaria test
- All outcomes will be measured by interviewing the participant after they make their decision about whether to be tested and which medicines to purchase.

2 BACKGROUND INFORMATION AND SCIENTIFIC RATIONALE

2.1 Background Information

Artemisinin combination therapies (ACTs) – the WHO-recommended first line therapy for uncomplicated malaria – have played a significant role in reducing global malaria mortality¹, but their overuse is rampant. In 2016 an estimated **216 million cases of malaria occurred worldwide, yet more than 400 million treatment courses of ACT were consumed**². Approximately 75% of global ACT demand is subsidized with international public funds from sources such as The Global Fund, DFID, and USAID³. Overconsumption of ACTs is an unnecessary drain on scarce public health resources and threatens the future sustainability of publicly-funded subsidies. In addition, it puts both present and future patients at risk; inappropriate treatment of a non-malaria illness with an antimalarial increases case fatality rates and contributes to population-wide drug pressure that accelerates the spread of drug resistance⁴⁻⁸.

Global over-consumption of ACTs is driven in large part by its increased distribution over-the-counter in private retail outlets as a result of publicly-funded subsidies directed to the private sector⁹. In 2015, **44% of all donor-funded ACTs consumed world-wide were distributed through the private retail sector** where studies have shown that **between 65-91% of ACTs dispensed for malaria are actually purchased by people without malaria**¹⁰⁻¹³. Malaria diagnostic testing is uncommon in the retail sector; fewer than 1 in 10 suspected cases are tested¹⁰. In the absence of parasitological testing, distinguishing fevers due to malaria from those due to other causes is not possible based on clinical presentation, and most fevers in malaria-endemic areas are assumed to be malaria-associated. As a result, presumptive treatment is prevalent and targeting ACTs to individuals with malaria infection is extremely poor.

Point-of-care malaria rapid diagnostic tests (RDTs), which have excellent sensitivity and specificity and are simple enough to be used by trained laypersons¹⁴, could expand the reach of diagnostics into the retail sector and help improve the rational use of antimalarials. Several studies have explored the potential role of RDTs in improving case management in the retail sector with mixed and often poor results. In most of these studies retail providers received case management training, followed by supportive supervision visits by researchers. In a few studies, the wholesale RDT price was partially or fully subsidized but retail providers were permitted to set their own price to the consumer and offer testing at their discretion^{15,16}. More often, outlets were required to provide testing free of charge or at a low fixed price and instruction to the outlet was quite rigid regarding when an RDT should be performed and an ACT should be dispensed¹⁷⁻²⁰. Providers were not explicitly incentivized to conduct RDTs.

All these studies shared two features – 1) ACTs were heavily subsidized for all customers and 2) there was no relationship between the RDT result and the ACT subsidy. This range of implementation strategies resulted in a wide range of testing uptake; between 7 - 100% of suspected malaria cases were tested²¹. Adherence to a negative malaria test was

inconsistent (between 1-40% of those with a negative test purchased an ACT) and often a significant portion of those testing positive, up to 70%, did not take an ACT²¹. Against this highly heterogeneous landscape of RDT implementation in the private retail sector, a few key lessons emerge. First, uptake of ACT is sensitive to the price of the drug²²; subsidies are necessary to ensure malaria-positive customers purchase an ACT even though higher prices could discourage malaria-negative clients from taking the drug. Second, uptake of RDTs appears to be more sensitive to price than uptake of ACT²². Patients are not willing to pay much to confirm a disease they often think they can diagnose themselves²³. Third, uptake of RDTs may also be sensitive to the price of the ACT, indicating that the relative price of the two commodities is important²⁴. Finally, fixed low prices of RDTs or ACTs are not sufficient to ensure adherence to test results^{21,24}.

In studies of RDT implementation in retail outlets, uptake of testing is sensitive to the relationship between the price of the test and the price of the ACT. As the price of the RDT relative to that of the ACT increases, testing rates drop precipitously. If the price ratio is high, customers will forgo the RDT and simply purchase an ACT, given its lower relative price. Qualitative studies in Uganda confirm that clients with limited resources prefer to spend money on drugs and prioritize testing only when presumptive treatment with the drug has failed²⁵. If the price of the ACT is higher than the RDT, then the investment in the RDT becomes a useful tool for discriminating between (more expensive) treatment options. When the price of the RDT is reduced to about a third of the cost of the ACT, uptake increases considerably. Our own work has shown that reducing the cost of the RDT from 40 Ksh (~\$0.50, the unsubsidized price) to 0 Ksh (fully subsidized) increases uptake by 25 percentage points²⁶. However, there is limited evidence to guide joint implementation of these commodities and to identify relative subsidy levels to maximize impact and minimize wastage. Since high malaria testing rates are a necessary pre-condition for ensuring that ACTs are targeted appropriately, we focus on identifying **the combination of RDT and ACT subsidies that maximizes the percent of clients receiving an RDT**, given a set amount of public funds earmarked to provide subsidized malaria commodities. We hypothesize that ACT subsidies that are conditional on the client receiving a malaria positive test can increase the uptake of malaria testing in the retail sector, while minimizing wastage of public funds. Furthermore, we hypothesize that while the uptake of testing will be sensitive to both the prices of the RDT and the ACT, a 50% subsidy on the RDT price will result in greater uptake of testing than increasing the subsidy on an ACT (conditional on a positive malaria test result) from 67% to 100%.

2.2 Scientific Rationale

We have chosen to conduct this study in Kenya for two main reasons. First, RDTs are not currently used in the retail sector in Kenya. Therefore, individuals presenting to an outlet for their illness would not have a prior expectation about receiving a test or have made a prior decision about whether they would like to receive a test. They will not have preconceived ideas about how much they should pay for an RDT. We would like to understand decision-making in the presence of a new tool (RDT) in a 'naïve' system.

Second, Kenya has maintained stable retail ACT prices for nearly five years. Although these prices are subsidized they are still likely to be a significant expense for households in the area. This offers two advantages – first, individuals know how much they expect to pay for an ACT before coming to the outlet and second, the ACT discounts we will offer (conditional on a positive test) are expected to be attractive to the customer (ie non-negligible).

Researchers have previously developed a theoretical framework of the decision-making behavior of individuals purchasing subsidized RDTs and anti-malarials. They performed a simulation of the model, with a range of estimated values for each of the parameters to predict the optimal subsidy levels for both ACT and RDTs. However, the predictions of the model depend crucially on individual beliefs that remain unknown: about the likelihood their illness is malaria, whether malaria diagnostic test results are correct, and about the effectiveness of the available anti-malarial treatments. This study provides a platform to empirically measure the decision-making behavior of clients under different subsidy programs, thus testing the validity of the model which could then be extrapolated to other contexts.

2.3 Potential Risks and Benefits

2.3.1 Potential Risks

The intervention proposed is a subsidy for diagnostic testing and the use of a conditionally subsidized ACTs in case of a positive test. The subsidy for testing will vary across clients but they can choose whether or not to use a test once they are enrolled and receive a subsidy offer. The subsidized ACT is offered only to patients with a positive test but, once again, the client is free to choose whether or not to use it. Participating in this study involves allowing us to record information about clients' malaria testing and treatment decisions. This includes the clients' decisions about whether to get tested for malaria using the RDT at the subsidized price, and whether to buy an ACT either at the subsidized price (if they test positive for malaria) or at the regular price (if they do not get tested or if they test negative). There is a small risk of breach of confidentiality of this information.

The RDTs to be used in this study are the same brand and test as those used by the Government of Kenya in public health facilities and in their community-based case management for malaria. Conducted properly, finger-sticks pose no greater than minimal risk to participants, including children. While unlikely, there is a small potential for excess bleeding or infection associated with finger pricks conducted in the course of administering an RDT. However, there is no alternative to a blood sample for diagnosing malaria and these risks are equivalent to the risk of seeking the same test from a facility or a community health worker. A finger prick blood sample is the least invasive and safest method to diagnose malaria. Several studies have demonstrated that RDTs can be safely and effectively used following training, even by those with limited formal training and no medical training. Study research assistants will be responsible for conducting RDTs and have been extensively trained in RDTs and dried blood spot collection. They have more than seven years of experience and have tested more than 1,000 people each. They are required to maintain updated CITI certificates and GCP training.

Study staff will be required to carry an identification certifying them as trained in RDT use. Study participants will be advised to contact the study coordinator, or to visit the closest health facility, in the case of any adverse events which may occur after the visit. All participants will be advised to go to a health facility if symptoms persist.

No venous blood will be drawn.

2.3.2 Known Potential Benefits

There is significant benefit to the client to knowing their malaria infection status prior to purchasing a drug. There is also a benefit to the client to be able to purchase an effective drug at a reduced, fixed price when they have a confirmed malaria infection, which may also reduce the likelihood that they would purchase an inappropriate or outdated therapy.

More broadly, there are important future benefits to rigorous testing of subsidy schemes that promote testing before treatment. This work will contribute to evidence-based policy making, improved access to malaria diagnosis and ultimately reduced potential for spread of antimalarial resistance.

3 OBJECTIVES

This objective of this experiment is to identify the combination of RDT and conditional (diagnosis-dependent) ACT subsidies that maximize the percent of clients receiving an RDT. We will test two different RDT price levels and two discounted ACT price levels in a factorial design. ACT discounts are conditional on a positive RDT result.

4 STUDY DESIGN

The study will be carried out in a random sample of 10 retail outlets that carry ACTs in the study area in western Kenya. The study population will be any individual presenting to the outlet with a malaria-like illness on randomly selected days. Children are eligible to be enrolled provided they are physically present and are accompanied by a parent or legal guardian. A research assistant will offer eligible participants a scratch card with a secret subsidy offer that will be revealed after the participant is enrolled. Using the scratch card, the participants will be randomized, in a 1:1:1:1 ratio, to one of four study arms shown in **Table 1**.

The research assistant will conduct RDTs for participants who choose to purchase an RDT. They will explain the results of the RDT to the participant, indicating whether the individual has malaria or not based on the test result. If the result is positive, the participant is entitled to an additional discount on their ACT purchase according to their scratch card. If the result is negative, the participant may purchase any medicine they choose, including an ACT at market price. Those who opt not to purchase an RDT may continue with their transaction as they choose, including purchasing a full-price ACT.

The participant will be interviewed before they scratch their card to record their symptoms, age, actions taken prior to coming to the outlet, and their experience with RDTs and ACTs in the past. We will also ask what drug they intend to buy when coming to the outlet. After they scratch the card and complete their transaction at the outlet (including purchasing an RDT if they choose), they will be interviewed again briefly to see what drugs they purchased. All scratch-card recipients will be interviewed regardless of whether or not they used their randomized offer. The two interviews combined will take approximately 20-30 minutes.

The primary outcome for this study is the customer's decision to purchase an RDT (yes/no). Using the 2x2 factorial design we will separately evaluate the effect of RDT price (2 levels: 50% vs. 0% subsidy) and of conditional ACT subsidies (2 levels: 100% vs. 67% subsidy) on the

ACT Price to client if he/she tests positive for malaria (Price for RDT negative or untested client = \$1.20)	RDT Price to client		Overall Proportion Tested*
	I. \$0.20 USD (50% subsidy)	II. \$0.40 USD (No Subsidy)	
I. \$0 USD (100% subsidy)	85%	70%	77.5%
II. \$0.10-0.40 USD (67% subsidy)	75%	60%	67.5%
Overall Proportion Tested*	80%	65%	

* Assuming the same sample size in each of the 4 study arms
 ** At current market prices, this subsidy level gives the following prices to the consumer: 6 [tablets@\\$0.10](#); 12 [tablets@\\$0.15](#); 18 [tablets@\\$0.20](#); 24 [tablets@\\$0.40](#).

primary outcome of testing uptake. A factorial design is optimal when we are interested in the independent effects of two interventions, in this case, the two types of subsidies. A 67% discount for an ACT gives the following price to the consumer for each age-specific dose based on current market price: 6 tablets –

\$0.10; 12 tablets - \$0.15; 18 tablets - \$0.20; 24 tablets - \$0.40.

Secondary outcomes include adherence to the RDT test result (defined as using an ACT if positive and using another drug if negative) and purchase of regular price ACT without a test. Due to the short time frame of recruitment (i.e. before entering outlet) to data collection (i.e. after leaving outlet), we do not anticipate missing outcome data.

5 Study Population

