7 STATISTICAL CONSIDERATIONS

7.1 Study Outcome Measures

The primary outcome measure is the decision to purchase an RDT before purchasing a drug.

Secondary outcome measures are:

2. Decision to purchase an ACT stratified by testing status
 - a. Positive mRDT
 - b. Negative mRDT
 - c. No malaria test

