7.4 Analysis Plan

All outcomes will be binary (e.g. tested – yes/no) and will be analyzed using a modified Poisson regression model^{27,28} with log link to estimate risk ratios (RRs) and identity link to estimate risk differences (RDs) in order to provide both relative and absolute measures of intervention effect. Such an approach assumes a Poisson distribution for the binary outcome and then 'fixes' the estimated standard errors to correct for model misspecification. We minimize clustering of outcomes by outlet with highly controlled intervention delivery and careful outcome measurements by research assistants. However, to account for possible clustering due to multiple individuals being randomized within different (randomly-sampled) outlets we will use a generalized estimating equations (GEE) approach with exchangeable working covariance matrix, Kauerman-Carroll correction and robust standard errors (to correct for model misspecification due to specifying a Poisson distribution)^{29,30}. The outcome will be regressed on

2 binary indicators, one each for the higher subsidy level of the two subsidies (50% RDT subsidy and 100% ACT subsidy), together with their interaction and a vector of potential confounder variables (e.g., age, gender) to account for possible imbalances between study arms. Although we hypothesize that there will be no evidence of a (statistical) interaction (see Sample Size details above), we will test for this interaction and, if significant, will separately report the effects of each subsidy conditional on levels of the other subsidy. In the absence of an interaction, we will estimate the overall ACT subsidy effect and the overall RDT subsidy effect by taking relative contrasts from the model. All analyses will be based on the intention-to-treat principle whereby all clients will be included in the analysis irrespective of whether they complied with the intervention.

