### 3 Outcomes, Exposures, and Additional Variables of Interest

All outcomes of interest are measured at the individual level and will be aggregated by each of the four groups. Importantly, not all outcomes will be defined on all individuals because some are “conditional” outcomes e.g. conditional on having taken a test. As a consequence, although the study design is a randomized experiment, we recognize that the analysis of some outcomes may be more subject to potential confounding than that of outcomes that are defined for all individuals.

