#### 3.2 Secondary Outcome(s)

Outcome	Description	Variables and Source	Specifications
ACT purchase among untested	Whether untested client chooses to take an ACT		Binary: yes/no
ACT purchase among test positive	Whether client chooses to take an ACT if test positive		Binary: yes/no

ACT purchase among test negative	Whether client chooses to take another drug or no drug if test negative		Binary: yes/no
Appropriate ACT use	Taking ACT if positive or not taking ACT if negative among the participants who had an RDT test		Binary: yes/no
Targeted ACT use	Taking ACT if positive or not taking ACT if negative among all participants, regardless of RDT test uptake		Binary: yes/no

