where  $Y_{ij}$  is an indicator of whether client  $j$  in outlet  $i$  ( $j=1, \dots, 84$ ;  $i = 1, \dots, 10$ ), chose to get tested for malaria in the retail outlet ( $=1$  if tested,  $0$  otherwise) and  $E(Y_{ij})$  is its expected value.  $\text{RDT\_SUBSIDY\_50\%}_{ij}$  is an indicator for whether the client received the lower RDT price of \$0.20 ( $=1$  if they received the offer of an RDT at \$0.20,  $=-1$  if they received the offer of an RDT at \$0.40) and  $\text{ACT\_SUBSIDY\_100\%}_{ij}$  is an indicator for whether the client received the higher ACT subsidy ( $=1$  if ACT price conditional on a positive test is \$0,  $=-1$  if ACT price conditional on positive test is \$0.40). Therefore,  $\text{RDT\_SUBSIDY\_50\%}_{ij} * \text{ACT\_SUBSIDY\_100\%}_{ij}$  represents an interaction term for clients who receive both the higher RDT and ACT subsidies or both the lower RDT and ACT subsidies ( $=1$  in two situations: a. RDT is offered at \$0.20 and ACT is offered at \$0 conditional on a positive test or b. RDT is offered at \$0.40 and ACT price conditional on positive test is \$0.40,  $=-1$  otherwise).  $\mathbf{w}_{ij}$  is a vector of potential confounder variables (e.g., age, gender, wealth, education) to account for possible imbalances between study arms. To account for possible clustering due to multiple individuals being randomized within 10 different (randomly-sampled) outlets we will use a generalized estimating equations (GEE) approach with

exchangeable working covariance matrix, robust standard errors (to correct for model misspecification due to specifying a Poisson distribution) and finite-sample correction (to obtain unbiased standard errors estimates using the Kauermann-Carroll method)[4, 5]. Regression diagnostics, including residual plots, will be used to verify model assumptions. Because all secondary outcomes are binary, we will use the same modelling approach to compare these outcomes.

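### Buying an ACT without a test is compared across arms only among clients who declined the test, so the comparison is not randomised and cannot show a fall in presumptive purchase

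*Protocol*

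**What the plan says.** - Protocol 4 (Study Design) names as a secondary outcome "purchase of regular price ACT without a test". Having no test is part of the event, and no denominator is stated.
- Protocol 7.1, like the synopsis, words the secondary outcome as "Decision to purchase an ACT stratified by testing status", with "c. No malaria test" as one of the three strata.
- SAP 3.2 carries only the stratum version: "Whether untested client chooses to take an ACT". Its one outcome defined on all participants, Targeted ACT use, scores ACT use against malaria status and is a different event.
- SAP 3 warns that "not all outcomes will be defined on all individuals because some are" conditional, and that "the analysis of some outcomes may be more subject to potential confounding than that of outcomes that are defined for all individuals".
- SAP 1.2.2 places ACT purchasing among untested, test-negative and test-positive clients under descriptive analysis. SAP 4.2 nevertheless says of the secondary outcomes that "we will use the same modelling approach to compare these outcomes".
- Protocol 7.4 states the intention-to-treat rule as "all clients will be included in the analysis irrespective of whether they complied with the intervention", and SAP 4.2 repeats it.

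**The concern.** Only a positive test earns the ACT discount, so an untested client who buys an ACT always pays the regular price. The Protocol 4 event is therefore simply buying an ACT without a test. A tested client can be scored no on it, and every randomised client then has a value. The SAP has no outcome or contrast for that event.

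The SAP instead models purchase within a subset that clients select after they have seen their price, and the subset is defined by the primary outcome. Clients who still decline a cheap test need not resemble those who decline a dearer one. Adjusting for age, gender, wealth and education does not restore the randomised comparison. Nor can this outcome be analysed on all clients, as the intention-to-treat statement promises.

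At stake is what the trial can say about presumptive ACT buying, which is the behaviour that the subsidies are meant to displace. A subsidy can reduce it by moving clients into testing, and an analysis restricted to those who stay untested does not count that route.

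**Working it through.** **Inputs.** Planned uptake by arm is 85%, 75%, 70% and 60% (design table in Protocol 4; SAP Table 1), with 210 clients per arm and 420 per factor level. The documents give no ACT purchase rate among untested clients, so every such rate below is an assumption.

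**The plan's own figure.** Protocol Table 2 gives totals of 838 (67.5% v 77.5%) and 374 (65% v 80%) for 90% power at two-sided 0.05. The pooled two-proportion formula is n per group = [1.96·√(2p̄(1−p̄)) + 1.2816·√(p₁(1−p₁) + p₀(1−p₀))]² / (p₁−p₀)². It gives 417 and 185 per group, so totals of 834 and 370, both close to the plan's. The uptake margins used here are therefore those behind the sample size.

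**Untested clients.** The untested share is one minus uptake: 15%, 25%, 30% and 40%, or 31.5, 52.5, 63 and 84 of 210. The total is 231 of 840.
- RDT factor: 20% v 35% (84 v 147 of 420).
- ACT factor: 22.5% v 32.5% (94.5 v 136.5 of 420).

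**The two versions.** Let u be the untested share and q the probability that an untested client buys an ACT, with subscript 1 for the higher subsidy and 0 for the lower.
- Untested-only RR = q₁/q₀.
- All-client RR = (u₁q₁)/(u₀q₀) = (u₁/u₀) × untested-only RR.
- u₁/u₀ is 0.20/0.35 = 0.57 (RDT) and 0.225/0.325 = 0.69 (ACT).
- The directions differ only when 1 < q₁/q₀ < u₀/u₁, so below 1.75 (RDT) or 1.44 (ACT).

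**Equal purchase among decliners (q₁ = q₀).** The untested-only RR is 1.00 for both factors, and the all-client RR is 0.57 and 0.69. For the RDT factor, at two-sided 0.05 with 420 v 420, unpooled Z-test and no clustering:

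| Assumed q | All-client, higher v lower subsidy | Power |
|---|---|---|
| 30% | 6.0% v 10.5% | about 66% |
| 50% | 10.0% v 17.5% | about 89% |
| 70% | 14.0% v 24.5% | about 97% |

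For the ACT factor at q = 50%, the rates are 11.25% v 16.25%.

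**Unequal purchase (assumed rates, expected z without clustering).**

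| Factor | q₀, q₁ | Untested-only RR (z) | All-client RR (z) |
|---|---|---|---|
| RDT | 50%, 60% | 1.20 (+1.47) | 0.69 (−2.25) |
| RDT | 60%, 75% | 1.25 (+2.31) | 0.71 (−2.26) |
| ACT | 50%, 60% | 1.20 (+1.50) | 0.83 (−1.12) |
| ACT | 30%, 45% | 1.50 (+2.33) | 1.04 (+0.18) |

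The last row lies outside the window (45/30 = 1.50, above 1.44), and both versions point the same way.

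**Mixed decliners.** Suppose the 15% who decline at any price buy an ACT 70% of the time, and the other decliners 35%. The all-client arm rates are then 0.15 × 0.70 + (u − 0.15) × 0.35 = 10.5%, 14.0%, 15.75% and 19.25%.
- RDT: all-client 12.25% v 17.5% (RR 0.70, z = −2.14); untested-only 61.25% v 50.0% (RR 1.23, z = +1.67).
- ACT: all-client 13.1% v 16.6% (RR 0.79, z = −1.43); untested-only 58.3% v 51.2% (RR 1.14, z = +1.08).

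**The case against.** **Protocol 4 may mean the stratum.** Its sentence is a summary, its first half is conditional on the test result, and it can be read as following the three strata of Protocol 7.1. The synopsis, Protocol 7.1, SAP 3.2 and shell Table B2 all use testing status. This stands in part. A reader might infer that the documents set two explicit, contradictory denominators. They do not: Protocol 4 states none, and the all-client reading is the natural one but is still a reading. What remains is an unreconciled definition, and the untested-only comparison would be weak whichever reading was meant.

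**The SAP already deals with it.** SAP 3 flags confounding, SAP 1.2.2 says descriptive, and Table B2 shows ACT and no ACT among untested clients by arm, so the all-client proportion follows by division. This also stands in part. But SAP 4.2 models the secondary outcomes, and Table B2 gives no pre-specified estimate that is adjusted and allows for clustering.

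**The all-client result repeats the primary outcome.** With equal purchase rates this is wholly right: 0.57 and 0.69 are ratios of untested shares, and the power shown above is power for the uptake effect. The untested-only RR of 1.00 is then a correct answer to a narrower question, whether behaviour differs among those who decline.

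**Opposite answers.** A reader might infer that the plan's own uptake makes the two versions contradict each other. Uptake alone gives no effect against a reduction. Reversal also needs an assumed purchase ratio inside the stated window. In the mixed-decliner example neither untested-only contrast is expected to reach 5% significance, and for the ACT factor neither version is.

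**Conclusion.** The point holds as a cheap improvement to one secondary outcome. The plan would model across arms a comparison that conditions on the complement of its primary outcome. That comparison is not randomised, and it cannot show a reduction in presumptive ACT purchase that comes through testing.

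At the planned uptake, the all-client risk ratio is 0.57 (RDT) or 0.69 (ACT) times the untested-only one, whatever the purchase rate. This rests only on the plan's expected arm proportions. With equal purchase among decliners the whole of the difference is testing uptake. Opposite directions need a purchase ratio between 1 and 1.75 (RDT) or 1 and 1.44 (ACT), on which the documents are silent. Reversal is therefore a possibility, not a prediction. The z and power values also assume the stated purchase rates and ignore clustering by outlet.

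The primary outcome, the sample size and the choice among subsidy combinations are not affected.

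**What to change.** - Add a row to SAP 3.2: bought an ACT without an RDT, yes/no, all randomised clients, with tested clients scored no.
- Fit the SAP 4.2 models to that row as the randomised comparison.
- Keep ACT purchase among untested clients as a descriptive result, in line with SAP 1.2.2 and Table B2, and exempt it from the modelling statement in SAP 4.2.
- Align the wording of Protocol 4 and 7.1 (and the synopsis) so that each version states its denominator.

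The cost is one table row, a few wording changes and one more fit of the existing models. Questions 4.1 and 5.1 of the participant questionnaire already collect the data. The downside is that the new outcome largely reflects testing uptake. It should be reported beside the primary result and the descriptive row, and not presented as independent evidence.
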